10.3. Laboratory Assessments

The continuous clinical laboratory assessments (hematology, chemistry, and urinalysis) will be summarized at each visit using descriptive statistics. The change from Screening will be provided at the end of SDP and end of OLE.

Shift tables will summarize changes in clinical laboratory assessments at the end of SDP and end of OLE with respect to baseline. Lab values are categorized into L1, low, normal, high, or H1 based on the lab reference range. L1 and H1 values are predefined per the lab vendor alert ranges and correspond to the extreme abnormal lower and higher ranges, respectively.

Abnormal laboratory assessments deemed clinically significant by the investigator will be reported as an adverse event.

A listing of subjects with abnormal value(s) according to the following criteria will be summarized using SAF:

- Any laboratory value that falls into the pre-defined low or high panic ranges (L1 or H1) per the Q2 Laboratory Range Chart.
- Alanine aminotransferase (ALT) or aspartate aminotransferase (AST) $\geq 3 \times$ Upper Limit of Normal (ULN) and total bilirubin $> 2 \times$ ULN
- AST or ALT $\geq 5 \times$ ULN,
- Creatinine ≥ 176
- Subjects positive for alcohol, urine drug screen or pregnancy assessments

All laboratory results, including pregnancy test, drug screen, and alcohol screen, will also be presented in subject data listings.

10.3.1. Laboratory Specific Derivation

- Multiple of upper limit of normal (ULN) = result / ULN

10.3.2. Laboratory Normal Reference Ranges

Quantitative laboratory measurements will be compared with the relevant laboratory reference ranges in SI units and categorized as:

- L1: result less than the low alert (L1)
- Low: result within the low alert (L1) and lower limit of normal (LLN) (L1 and LLN limit included)
- Normal: result within the laboratory normal reference range (LLN and ULN limit included)
- High: result within the ULN and high alert (H1) (ULN and H1 limit included)
- H1: result greater than the high alert (H1)

10.4. Vital Signs

The following vital signs measurements will be reported for this study.

- Sitting systolic blood pressure (SBP), (millimeter of mercury [mmHg])
- Sitting diastolic blood pressure (DBP) (mmHg)
- Sitting heart rate (beats per minutes [bpm])
- Sitting respiratory rate (breaths/min)
- Body Temperature (°C)
- Weight (kg)
- Height (cm)
- BMI (kg/m²) [derived]
- Pulse Oximetry (%) Screening and PK Nights only)

These vital signs (with the exception of the BMI which will be calculated programmatically) will be measured during the screening visit and each in-clinic scheduled visit. Height (cm) will be obtained at screening visit only.

The following summaries will be provided for vital signs data across all study periods

- Observed and change from baseline by visit
- Incidence of markedly abnormal criteria by visit

10.4.1. Vital Signs Markedly Abnormal Criteria

Markedly abnormal quantitative vital signs measurements will be identified in accordance with the following predefined markedly abnormal criteria as specified in Table 5.

Table 5: Vital Signs Predefined Markedly Abnormal Criteria

Variable (unit)	Low	High
SBP (mmHg)	≤ 90 mmHg AND change from baseline ≤ -20 mmHg	≥ 180 mmHg AND change from baseline ≥ 20 mmHg
DBP (mmHg)	≤ 50 mmHg AND change from baseline ≤ -15 mmHg	≥ 105 mmHg AND change from baseline ≥ 15 mmHg
Heart rate (bpm)	≤ 50 bpm AND change from baseline ≤ -15 bpm	≥ 120 bpm AND change from baseline ≥ 15 bpm
Weight (kg)	percentage change from baseline $\leq -10.0\%$	percentage change from baseline $\geq 10.0\%$

Variable (unit)	Low	High
Temperature (°C)	≤ 35.0 °C	≥ 39.0 °C

Note: bpm: Beats per minute. DBP: Diastolic Blood Pressure. kg: kilogram. mmHg: Millimeter of mercury. SBP: Systolic Blood Pressure

10.5. ECG

A standard 12-Lead ECG will be recorded with the subject resting in supine for at least 5 minutes. ECGs will be performed during the Screening visit, end of the SDP, end of the DBRW visit, and end of OLE visit or early termination visit. Results from the central ECG core lab will be included in the reporting of this study. The following ECG parameters will be reported:

- PR Interval (msec)
- RR Interval (msec)
- QRS Interval (msec)
- QT Interval (msec)
- QT Bazett's correction (QTcB) Interval (msec) [derived]
- QT Fridericia's correction (QTcF) Interval (msec) [derived]
- Mean HR (bpm)
- Sinus Node Rhythms and Arrhythmias
 - Normal Sinus Rhythm
 - Sinus Arrhythmia
 - Sinus Tachycardia
 - Sinus Bradycardia
- Overall assessment of ECG:
 - Normal
 - Abnormal

The following summaries will be provided for ECG data across the study:

- Observed and change from screening by visit (for quantitative measurements)
- ECG parameters results will be listed over time.

10.5.1. ECG Specific Derivations

- $QTcF \text{ (msec)} = \sqrt[3]{\frac{QT \text{ (ms)}}{RR \text{ (ms)}}} / 1000$

$$\bullet \quad QTcB \text{ (msec)} = \frac{QT \text{ (ms)}}{\sqrt{RR \text{ (ms)}/1000}}$$

10.5.2. ECG Abnormal Criteria

Abnormal quantitative ECG measurements will be identified in accordance with the following predefined markedly abnormal criteria (FDA 2005)

Observed values for QT interval, QTcB interval and QTcF will be classified as follows at each time point:

- > 450 msec
- > 480 msec
- > 500 msec

Change from baseline for QT interval, QTcB interval and QTcF will be classified as follows:

- >30 msec increase from baseline
- >60 msec increase from baseline

A listing of subjects meeting markedly abnormal criteria as well as a listing of subjects with abnormal ECG overall assessment will also be provided based on the SAF.

10.6. Other Safety Endpoints

10.6.1. Columbia-Suicide Severity Rating Scale

The C-SSRS is a widely used measure of suicidal ideation and behavior. The instrument reliably predicts a potential suicide attempt in those who had previously attempted suicide and is able to determine clinically meaningful points at which a person may be at risk for an impending suicide attempt (Posner *et al* 2011, Nilson *et al* 2012).

The Screening/Baseline version of the C-SSRS will be administered to subjects at screening visit.

The Since Last Visit version of the C-SSRS will be administered to subjects at every scheduled in-clinic and phone visit after the screening visit up to the Safety Follow-up visit.

The following summaries will be provided for the C-SSRS data by visit across all study periods by Baseline Medication Group and by treatment group for summaries during the DBRW:

- Number and percentage of subjects with any suicidal ideation (i.e., having responded yes to any of the 5 types of suicide ideation) as well as broken down by type of suicidal ideation
- Number and percentage of subjects with any suicidal behavior ((i.e. having responded yes to any of the 4 or 5 types of suicidal behavior, as applicable) as well as broken down by type of suicidal behavior
- Number and percentage of subjects with any suicidal behavior or any suicidal

ideation; a subject having reported both suicidal behavior and suicidal ideation will be counted only once

- Number and percentage of subjects with self-injurious behavior without suicidal intent.

Missing data will not be imputed. All C-SSRS parameters will be presented in the subject data listing.

10.7. Safety and COVID-19 Considerations

10.8.1. Alternative methods for safety assessments

For remote visits, the Investigator will remain in contact with the subject via telephone to discuss adverse events, as well as to evaluate efficacy and tolerability of the prescribed dose of study drug. See Appendix 5 below for further details on performing remote assessments. Sites were instructed to collect data for selected safety assessments (e.g. lab, ECG) when the subject is next able to safely return to an on-site visit, even if those assessments would not normally be done at that visit. Note that all protocol deviations due to changes in how assessments are collected will be recorded and labeled as related to COVID-19 mitigations, as per “*The Guidance*”.

10.8.2. Assessment of safety due to COVID-19 considerations

Safety summaries will combine data that is collected on-site and remotely (e.g. exposure, adverse event, and CSSR-S). Safety assessments that were not done due to COVID-19 restrictions will be excluded from the summaries. A total number of assessments not done due to COVID-19 restrictions will be provided. A summary table of all protocol deviations relating to COVID-19 restrictions will be included.

11. PHARMACOKINETICS

The dosing regimen during the PK evaluation will be the subject’s currently assigned treatment regimen. Subjects will take their dose(s) at similar conditions to those normally followed at home. Blood samples for subjects administering JZP-258 twice nightly will be collected at 0 (pre-dose), 0.5, 0.75, 1, and 1.5 hour after dosing for each dose administered, with the last sample collected at 8 hours after the first dose. Blood samples for the once nightly dosing regimen will be collected at 0 (pre-dose), 0.5, 0.75, 1, 1.5, 2, 4, and 8 hours after dosing. Blood samples must be collected within \pm 5 minutes of the protocol-specified time points for those time points up to 1 hour after dosing and within \pm 15 minutes of the protocol-specified time points for those longer than 1 hour after dosing (e.g., 4 and 8 hours post dose). Actual times of dose administration, blood samples for oxybate concentrations, and meals/snack times must be precisely recorded on the source document and in the electronic case report form.

11.1. Pharmacokinetic Endpoints

PK will be evaluated using noncompartmental analysis as data permits. This section further describes the definition of the PK endpoints.

- C_{\max} is defined as the maximum plasma drug concentration over post dose samples.
 - For the twice nightly regimen, $C_{\max 1}$ is defined as the maximal concentration from post the 1st evening dose up to and including the 2nd evening pre-dose concentration. $C_{\max 2}$ is defined as the maximal concentration post 2nd evening dosing.
 - For once nightly, C_{\max} is defined as the maximum plasma drug concentration during the 8-hour sampling period post dose.
- T_{\max} is defined as the elapsed time from administering the dose to the maximum drug concentration, measured in hours. Values are calculated for the following:
 - For the twice nightly regimen, $T_{\max 1}$ is time to $C_{\max 1}$. $T_{\max 2}$ is time to $C_{\max 2}$.
 - For once nightly, T_{\max} is defined as the time to reach C_{\max} .
- AUC is defined as the area under the plasma concentration versus time curve as calculated by the linear trapezoidal method for the following intervals
 - For the twice nightly regimen, AUC₁ for the first dosing interval (using samples from initial dose to 2nd evening pre-dose) and AUC₂ for the second dosing interval (using samples post 2nd dose), and AUC_{0-t_{last}} for total AUC following both doses where *t_{last}* refers to the last measurable plasma concentration.
 - For once nightly, AUC_{0-t_{last}} will be estimated.

Scheduled pre-dose samples will have 0 used for the elapsed time from dosing for calculation of AUC values.

- $t_{1/2}$ is defined as the terminal half-life and is based on a minimal of 3 last plasma concentrations in the terminal phase of the concentration-time profile, if data permit.

11.2. Pharmacokinetic Analyses

Descriptive statistics including number of subjects, mean, SD, minimum, median, maximum, coefficient of variation, geometric mean, and geometric SD will be used to summarize concentration data and PK parameters for subjects based on stable vs. nonstable doses and based on dose regimens (e.g., dose, once vs. twice nightly), as appropriate. The PK night dose regimen will be compared to the dose regimen during the SDP and if the dose regimen is the same then the subject will be considered on a stable dose. If they are not the same dose regimen then the subject will be categorized as a nonstable dose. For all graphs and summary statistics, if there are less than 3 subjects on a nonstable dose per regimen then outputs will combine stable and nonstable doses.

All statistical summaries and displays will be based on scheduled sampling times unless there are significant deviations of actual sampling times from scheduled sampling times. In calculation of the concentration summaries and for the calculation of PK parameters, if concentration values are below the limit of quantitation they will be set to zero

Subjects who are included in the PK summary but have missing data for a particular endpoint will not be included in the analysis for that endpoint. Unused data, measurements from excluded subjects, unscheduled collections, or extra measurements will not be included in the summaries, but will be presented in the subject listings.

Plasma oxybate concentration-time data will be graphically displayed as individual and as mean (with SD) based on stable vs. nonstable doses and based on dose regimens (e.g., once and twice nightly), as appropriate, using linear and log scales.

If data permits (at least 10 subjects), evidence of dose proportionality for $AUC_{0-t_{last}}$ and the combined outcome of C_{max} (for once nightly regimen) and C_{max1} (for twice nightly regimen) will be investigated using the power model (Smith et al, 2000). Both models will include observations from once and twice nightly dose regimens.

Specifically,

$\ln(\text{PK parameter}) = \beta_0 + [\beta_1 \cdot \ln(\text{dose})]$, where β_0 is the intercept and β_1 is the slope

For $AUC_{0-t_{last}}$, dose will be included as total nightly dose. For the model of C_{max}/C_{max1} , dose will be included as total nightly dose for observations from once nightly and as first dose for observations from twice nightly.

Dose proportionality is declared when the 90% CI for β_1 lies completely within the critical region defined as:

$$1 + \frac{\ln(\theta_L)}{\ln(r)} < \beta_1 < 1 + \frac{\ln(\theta_H)}{\ln(r)}$$

where r represents the dose ratio between the minimum and maximum dose, $\theta_L = 0.8$, and $\theta_H = 1.25$.

Listings will summarize the dose regimen, oxybate concentration-time data by scheduled and actual sampling times, PK parameters, last meal and/or snack time.

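### SAP 11.2 sets oxybate concentrations below the quantitation limit to zero yet summarises them by geometric mean and geometric SD, and the text does not keep such values out of the half-life points

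*SAP*

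**What the plan says.** SAP 11.2 (Pharmacokinetic Analyses) has two rules that meet at any time point with a BLQ concentration.

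- Summary statistics: "coefficient of variation, geometric mean, and geometric SD will be used to summarize concentration data and PK parameters".
- BLQ values: "if concentration values are below the limit of quantitation they will be set to zero". The SAP states this for the concentration tables and for the derived parameters alike, so one rule serves both.

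SAP 11.1 (Pharmacokinetic Endpoints) says that half-life "is defined as the terminal half-life and is based on a minimal of 3 last plasma concentrations in the terminal phase", if the data allow it. It does not say that those concentrations must be quantifiable. A restriction of that kind appears only in the AUC definition, where the end time of AUC0-tlast "refers to the last measurable plasma concentration".

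The exclusion rule in SAP 11.2 is for subjects with missing data on an endpoint. A BLQ result that has been given the value zero is not missing. Protocol 9.8.3 and 9.9.6 contain no BLQ rule. Protocol 6.13 names a validated LC/MS/MS assay without a lower limit of quantitation.

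**The concern.** A geometric mean is defined through logarithms, and zero has none. Followed literally, the SAP therefore asks for a statistic that collapses to 0 and for a geometric SD that does not exist, as soon as one subject is BLQ at that time point. In practice, code that takes logs is likely to turn the zeros into missing values. The table would then show a geometric mean over the quantifiable subjects beside an arithmetic mean over all subjects, with different denominators and no instruction to say so.

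The half-life wording has a related gap. The zero rule covers PK parameters, and the last few samples are the ones most likely to be BLQ.

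What is at stake is the readability of the pre-dose and tail concentrations, and of some half-lives, in a substudy that serves a stated secondary objective. It enrols up to 30 subjects, with about 24 expected to be evaluable (protocol section 4), and its results are split further by regimen and dose stability.

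**Working it through.** The documents state no figure on this point, so there is none to reproduce. The check follows the rule through.

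**Inputs from the documents**
- BLQ = 0 and geometric statistics for concentrations (SAP 11.2); half-life and tlast definitions (SAP 11.1).
- Once-nightly sampling (SAP 11): "Blood samples for the once nightly dosing regimen will be collected at 0 (pre-dose), 0.5, 0.75, 1, 1.5, 2, 4, and 8 hours after dosing".
- Twice nightly: the last sample is 8 h after the first dose (SAP 11), and the second dose follows 2.5 to 4 h after the first (protocol 5.3.2).
- About 24 evaluable PK subjects (protocol section 4).
- For scale: Cmax 92.58 µg/mL and median Tmax 1.00 h for 4.5 g JZP-258, fasted (protocol 1.2.2.2).

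**Assumptions, not in the documents**
- Lognormal concentrations with log-SD 0.8, and 0.5 and 1.0 as a range.
- Mono-exponential decline from the peak, with half-life 0.5 to 1.5 h.

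**1. Geometric mean with zeros kept.** GM = exp(mean of ln C), or equivalently the n-th root of the product. One zero among 24 makes the product 0, so GM = 0. The geometric SD needs ln 0 and is undefined.

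**2. Geometric mean with zeros lost on taking logs.** Place 24 values at normal quantiles (i − 0.5)/24 and treat the lowest k as BLQ. The ratio of the reported to the full-sample GM is exp(log-SD × mean z of the remaining values).

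| BLQ of 24 | n used | mean z | ratio, log-SD 0.5 | ratio, log-SD 0.8 | ratio, log-SD 1.0 |
|---|---|---|---|---|---|
| 1 | 23 | 0.089 | 1.05 | 1.07 | 1.09 |
| 4 | 20 | 0.294 | 1.16 | 1.27 | 1.34 |
| 8 | 16 | 0.538 | 1.31 | 1.54 | 1.71 |
| 12 | 12 | 0.788 | 1.48 | 1.88 | 2.20 |

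Over the same range, at log-SD 0.8, the arithmetic mean with zeros kept falls to 0.99, 0.96, 0.89 and 0.78 of its full-sample value. The two means in one table therefore move in opposite directions.

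**3. Where BLQ values could arise.** For a once-nightly subject, C(8 h) = 92.58 × 2^(−7/half-life). This gives 0.006, 0.14, 0.72 and 3.6 µg/mL for half-lives of 0.5, 0.75, 1.0 and 1.5 h. Whether any of these is BLQ depends on the unstated quantitation limit. For a twice-nightly subject the last sample falls 8 − 4 = 4 h to 8 − 2.5 = 5.5 h after the second dose, so it is less exposed.

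**4. Half-life.** The last three once-nightly samples are 2, 4 and 8 h. With C(8 h) = 0 the log-linear fit has no solution. If the zero were replaced by 0.01, 0.1 or 1 µg/mL, a half-life assumed to be 0.75 h would come out as 0.50, 0.70 or 1.20 h. If the BLQ sample is left out, the 1.5, 2 and 4 h samples remain and return 0.75 h.

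**The case against.** Several limits on this point stand.

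- **Half-life.** A reader might infer that the terminal fit will contain a zero, or that half-lives will fail. The documents do not support that. A zero cannot be a point in a log-scale fit. SAP 11.1 restricts half-life to the terminal phase and makes it conditional on the data allowing it, so an analyst is free to drop the sample and probably would. With a median Tmax of 1.00 h, a once-nightly subject would still have three samples after the peak. What remains is that the exclusion is written for AUC0-tlast and not for half-life.
- **Frequency.** A reader might infer that the 8 h geometric means will be zero or roughly doubled. No quantitation limit or BLQ rate is given, and the ratios of about 1.5 to 2.2 need half the subjects to be BLQ. With one BLQ subject in 24 the distortion is 1.05- to 1.09-fold.
- **Pre-dose samples.** If every pre-dose value is BLQ, the mean, median, minimum and maximum are all 0 in any case, and no PK conclusion rests on the geometric mean there.
- **Transparency.** The median and arithmetic mean are reported alongside and keep the zeros, and SAP 11.2 lists the individual concentrations.

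These points shrink the concern but do not remove it. Two rules in one section still cannot both be carried out where a BLQ value occurs, and the SAP does not say which gives way.

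**Conclusion.** The point holds as a minor defect in the SAP. For concentration summaries it is a rule that fails when followed: any BLQ value gives a geometric mean of 0 and no geometric SD. The likely workaround overstates the geometric mean by about 1.07-fold (1 of 24 BLQ) to 1.9-fold (12 of 24), assuming lognormal concentrations with log-SD 0.8. The exposed samples are most plausibly pre-dose and once-nightly 8 h, subject to a quantitation limit that the documents do not give. For half-life the defect is only an omission.

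It would go too far to conclude that the secondary PK objective is undermined. Cmax is unaffected while it is positive, AUC0-tlast stops at the last measurable value, and the dose-proportionality models use those parameters. The PK results are descriptive, and no efficacy test or power statement changes.

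**What to change.** Amend the wording of SAP 11.1 and 11.2:

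1. Keep BLQ = 0 for arithmetic summaries and for pre-dose samples.
2. Report the number and percentage of BLQ values at each time point.
3. Mark the geometric mean and geometric SD as not calculated where BLQ values are present, and rely on the median there. Alternatively, set a BLQ fraction in advance above which they are not calculated, and show the n used below it. The second form avoids losing the statistic for a single BLQ value in 24. The choice is partly preference, but it should be written down.
4. Limit the half-life fit to quantifiable concentrations after Tmax.

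The cost is a few lines of SAP text and some table cells that show a BLQ count instead of a geometric mean. No data collection or sample size changes.

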Appendix 1: Programming Conventions for Outputs

Outputs will be presented according to the following:

Paper size, orientation, and margins: The size of paper will be Letter. The page orientation will be landscape; Margins should provide at least 1 inch (2.54 centimeters) of white space all around the page, regardless of the paper size.

Fonts: The font type ‘Courier New’ will be used as a default for tables and listings, with a font size of 8. The font color will be black. No **bolding**, underlining, *italics* or subscripting will be permitted.

Super-scripts will be avoided, unless absolutely necessary. Single spacing will be used for all text.

SDTM Terminology: When possible, SDTM controlled terminology (e.g., race) will be used in the tables, listings and figures outputs.

Dates & Times

Depending on data available, dates and times will take the form yyyy-mm-ddThh:mm:ss.

Spelling Format

English US, with the exception of the MedDRA SOCs and PTs for which British English will be used.

Presentation of Treatment Groups

For outputs by Baseline Medication Group, the groups will be presented as follows and in that order:

Group Number	Baseline Medication Group	For Tables, Figures, and Listings
1	Subjects on Xyrem only	Xyrem Only
2	Subjects on Xyrem and an additional stimulant or alerting agent	Xyrem + Stimulant or AA
3	Subjects on a stimulant or alerting agent only	Non Xyrem Stimulant or AA Only
4	Subjects not currently taking	Treatment Naïve

	Xyrem or a stimulant or alerting agent	
--	--	--

For outputs by randomized treatment group, the groups will be presented as follow and in that order:

Randomized Treatment Group	For Tables, Figures, and Listings
JZP-258	JZP-258
Placebo	Placebo

Number of Decimal Places to Be Presented

For descriptive statistics, the same number of decimal places as in the raw data will be presented when reporting minimum and maximum, 1 more decimal place than in the raw data will be presented when reporting mean and median, and 2 more decimal places than in the raw data will be presented when reporting SD. If the raw data has 3 decimals or more, 3 decimals will be presented for mean, SD, median, minimum, and maximum.

For percentages, 1 decimal place will be presented.

For LS means, LS mean differences, SEs, and CIs, 2 more decimal places than in the raw data will be presented. If the raw data has 3 decimals or more, 3 decimals will be presented.

For p-values, 4 decimal places will be presented.

Listings

All data collected on the electronic case report form will be presented in the data listings. The listings will be ordered by the following (unless otherwise indicated in the shells): randomized treatment group, Baseline Medication Group, subject number, date (where applicable), and time (where applicable).

For listings where non-randomized subjects are included, these will appear in a category after the randomized treatment groups labeled 'Not Randomized'.

